#### 7.4 **Efficacy Evaluation**

#### 7.4.1 Datasets Analyzed

All efficacy summaries will be based on the IEAS. A data listing of subjects excluded from the IEAS, to include the reason for exclusion, will be presented.

#### 7.4.2 Measurements of Treatment Compliance

Not applicable. This is a single dose study, administered by site staff.

#### 7.4.3 Primary Efficacy Endpoint Analysis Methods

For each uptake threshold (Mild or Higher Uptake, Moderate or Higher Uptake, Marked Uptake), the number and percentage of True Positives, False Positives, True Negatives, and False Negatives will be presented for each reader. Sensitivity, Specificity, PPV and NPV will be calculated, with estimates and the 95% exact confidence intervals displayed.

The summary will be presented for subject-level performance (based on reference lesion data), and repeated for lesion-level performance (based on data of all sampled lesions).

For lesion-level performance, confidence intervals will be calculated based on the methodology described by Zhou et al., to account for clustering within subjects. The formula for PPV is:

$$\widehat{PPV} = \sum_{P} TP_{p} / \sum_{P} Pos_{p}$$

$$\widehat{Var}(\widehat{PPV}) = \frac{1}{P(P-1)} \sum_{P} \binom{Pos_{p}}{Pos}^{2} (\widehat{PPV_{p}} - \widehat{PPV})^{2}$$

With:

 $\boldsymbol{P}$ : (number of) Patients

 $\begin{array}{ll} p & : \text{ individual patient} \\ Pos_p & : \text{ Number of positive regions for patient } p \\ \hline Pos & : \text{ Number of true positive regions for patient } p \\ \hline Pos & : \text{ Number of true positive regions for patient } p \\ \hline Pos & : \text{ Mean cluster size} \end{array}$ 

 $\widehat{PPV_p} = TP_p/Pos_p$ : Patient PPV

The example in Zhou et al. is coded in SAS in Appendix 1.

In addition, pairwise inter-rater agreements at the lesion level for the 3 readers will be tabulated for the F-fluciclovine uptake. The proportions of agreement vs disagreement, Cohen's Kappa and the associated 95% confidence interval will be calculated.

Confidential Page 16 of 22 The results of these analyses will be reviewed by the separate Image Interpretation Committee as described in the study protocol to determine image interpretation criteria based on visual reads.

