# 6.4.1.2 Secondary Efficacy Variables

Secondary efficacy endpoints include the following:

- Diagnostic performance (sensitivity, specificity, PPV and NPV) of different thresholds of quantitative and dynamic measures of lesion F-fluciclovine uptake versus SoT derived from central histopathological analysis of all lesions, at subject-level and lesion-level.
- Subject-level sensitivity, specificity, PPV and NPV of F-fluciclovine PET scan for detecting recurrent brain metastases, based on combined application of the established image interpretation criteria.
- Lesion-level sensitivity, specificity, PPV and NPV of F-fluciclovine PET for detecting recurrent brain metastases, based on combined application of the established image interpretation criteria.

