# 7.4.4 Secondary Endpoint Analysis Methods

In order to establish other image interpretation criteria for  $^{18}\text{F}$ -fluciclovine PET in detecting recurrent brain metastases, receiver operating characteristic (ROC) analysis of SoT against the quantitative measures of lesion  $^{18}\text{F}$ -fluciclovine uptake will be performed for each reader. A ROC curve will be produced for lesion SUV $_{\text{max}}$ , SUV $_{\text{peak}}$ , TBR $_{\text{max}}$  and TBR $_{\text{peak}}$ , with each point corresponding to a specific threshold, eg.  $\geq$  SUV $_{\text{max}}$  value vs < SUV $_{\text{max}}$  value. The AUC of each curve will be calculated using the trapezoidal method and will be annotated on the plot. Sensitivity, specificity, PPV, and NPV will be listed for each value of lesion SUV $_{\text{max}}$ , SUV $_{\text{peak}}$ , TBR $_{\text{max}}$  and TBR $_{\text{peak}}$ .

For TBRmax and TBRpeak, pairwise inter-rater agreement will be assessed using Pearson correlation coefficients.

For dynamic measures of lesion F-fluciclovine uptake represented by TAC type, applying each TAC category as a diagnostic criterion, estimates and the 95% exact confidence intervals for sensitivity, specificity, PPV and NPV for each of the 4 TAC types will be calculated and presented, by reader, on both subject and lesion levels. Lesion-level confidence intervals will be based on the method by Zhou et al..

In addition, pairwise inter-reader agreements at the lesion level for the 3 readers will be tabulated for TAC type. The proportions of agreement vs disagreement, Cohen's Kappa and the associated 95% confidence interval will be calculated.

These analyses will be reviewed by the separate Image Interpretation Committee to determine a set of image interpretation criteria based on the quantitative and dynamic measures.

Subsequently, for the diagnostic performance secondary endpoints, estimates and the 95% exact confidence intervals for sensitivity, specificity, PPV and NPV will be calculated based on the recommended thresholds from the following combination of interpretation criteria (if featured in the interpretation criteria):

- 1. Visual assessment of level of lesion F-fluciclovine uptake
- 2. Strongest performing quantitative measure (based on ROC analysis)

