#### 7.4.5.5 Examination of Subgroups

The summaries of different thresholds of lesion F-fluciclovine uptake, and time activity curve types, on visual reads vs standard or truth, at the lesion-level, will be repeated on the following subgroups:

Primary Tumor Type:

- Melanoma
- Breast
- Lung Cancer (NSCLC and SCLC)
- Gastrointestinal (Colorectal and Pancreatic)
- Genitourinary (Bladder, Kidney, Testes)
- Non-Lung/Breast/Melanoma

Concurrent Immunotherapy:

- Received Concurrent Immunotherapy
- Did Not Receive Concurrent Immunotherapy

Calculations will only be performed when there are at least 10 observations in the subgroup.

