## 7.6 Determination of Sample Size

Up to 40 subjects are planned for enrollment. The sample size is not calculated based on formal statistical hypothesis testing criteria, but is estimated to provide sufficient numbers of subjects and data to establish image interpretation criteria.

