## Appendix 1: SAS program to reproduce data in Zhou et al.

```
data one;
input TN
              No_Polyps;
Cards;
1
       1
2
       2
2
       2
1
       1
2
2
       2
1
       1
1
       1
1
       1
1
2
       2
0
       1
2
2
       2
1
       1
1
1
       1
2
       2
1
0
       2
1
       1
2
       2
2
       2
2
0
       1
;;;;
run;
proc sql;
   create table two as
      select
         TN,
         No_Polyps,
         TN/No_Polyps as Sei_hat,
         Se hat,
         No_Polyps/mNo as Ni_N,
         (calculated Ni N) * (calculated Ni N)
              * (calculated Sei hat-Se hat)* (calculated Sei hat-Se hat) as fc,
         sum(calculated fc) as sfc,
         calculated sfc/(n*(n-1)) as varSe_hat
      from
          (select
            sum(TN) as sTN,
            sum (No Polyps) as sNo,
            mean(No_Polyps) as mNo,
            count(*) as n,
            calculated sTN/calculated SNo as Se_hat
            from one ) as o,
         one;
quit;
data final;
   set two;
   if n = 1;
   keep Se hat varSe hat;
run;
```

Confidential Page 22 of 22

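### The lesion-level cluster variance is exactly zero at an estimate of 0% or 100%, and the SAP does not say what interval is then reported

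*SAP*

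**What the plan says.** SAP 7.4.3 first sets the general rule for the primary endpoint: "Sensitivity, Specificity, PPV and NPV will be calculated, with estimates and the 95% exact confidence intervals displayed". For lesion-level results it then substitutes another method: "For lesion-level performance, confidence intervals will be calculated based on the methodology described by" a cited textbook, for the stated purpose of handling clustering within subjects. It prints the pooled estimate and its variance, using PPV as the example.

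Appendix 1 codes the same variance, ending in "calculated sfc/(n*(n-1)) as varSe_hat", and keeps only the estimate and the variance. Neither place shows how the variance becomes a 95% interval or what to report when it is zero.

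Section 7.4.4 extends the method to the time-activity-curve (TAC) types: "Lesion-level confidence intervals will be based on the method by" the same text. Further down, for the combined interpretation criteria, it says only: "Subsequently, for the diagnostic performance secondary endpoints, estimates and the 95% exact confidence intervals for sensitivity, specificity, PPV and NPV will be calculated". One of those endpoints is at lesion level; section 6.4.1.2 lists it as "Lesion-level sensitivity, specificity, PPV and NPV of" the PET scan.

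On size, section 7.6 says "Up to 40 subjects are planned for enrollment". Section 7.4.5.5 repeats the lesion-level threshold and TAC summaries in subgroups, with this limit: "Calculations will only be performed when there are at least 10 observations in the subgroup".

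**The concern.** A between-subject variance cannot express uncertainty when every subject gives the same result. If all tumour lesions meet the 'Mild or higher' threshold, observed sensitivity is 100% and the estimated variance is zero, however few lesions there are. The reported interval would be 100% to 100%, or could not be computed.

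Such results are most likely at the extreme thresholds (sensitivity at 'Mild or higher', specificity at 'Marked') and in small subgroups. Someone would then have to choose an interval after seeing the result, or the Image Interpretation Committee would see a degenerate lesion-level interval beside a proper exact one at subject level. The SAP's Introduction says that analyses are described in advance so that such post hoc decisions are avoided.

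**Working it through.** The SAP states no numerical interval for this point, so there is no figure to reproduce. The check takes the printed formula and applies it.

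**Formula (7.4.3, Appendix 1).** With P subjects, n_p lesions in the denominator for subject p, mean cluster size m, subject proportion r_p and pooled proportion r:

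Var(r) = [1 / (P(P−1))] × Σ (n_p/m)² (r_p − r)²

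**At the boundary.** If r = 1, every contributing subject has r_p = 1, so each term is 0 and Var = 0. The same holds at r = 0. An interval r ± 1.96 SE is then 100–100% or 0–0%. A logit interval is undefined, because the logit of 0 or 1 is infinite.

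**Numerical check.** Assume 24 subjects, 20 with one lesion and 4 with two (28 lesions, m = 28/24 = 1.167).

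- All lesions correct: Var = 0.
- One single-lesion subject wrong: r = 27/28 = 0.964.
  - 19 correct single-lesion subjects: 19 × 0.735 × 0.0357² = 0.018
  - 4 correct two-lesion subjects: 4 × 2.939 × 0.0357² = 0.015
  - the wrong subject: 0.735 × 0.964² = 0.683
  - total 0.716; Var = 0.716/(24 × 23) = 0.00130; SE = 0.036.

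One lesion therefore moves the SE from 0.036 to exactly 0.

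**How often.** The cap is 40 subjects (7.6). True accuracy, denominators and clustering are assumptions. With one lesion per subject, the chance of an observed 100% is (true rate)^(number of subjects):

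| True rate | Subjects in denominator | P(variance = 0) |
|---|---|---|
| 95% | 24 | 0.95^24 = 29% |
| 90% | 16 | 0.90^16 = 18.5% |
| 85% | 24 | 0.85^24 = 2.0% |
| 80% | 24 | 0.80^24 = 0.5% |
| 95% | 6 (subgroup of 10 observations, 6 of them tumour) | 0.95^6 = 74% |
| 90% | 6 (same subgroup) | 0.90^6 = 53% |

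**With clustering.** Beta-binomial simulation with 15% of subjects having two lesions, intracluster correlation (ICC) 0.5 and 20,000 runs per scenario gave zero variance in 26% of runs (true 95%, 24 subjects) and 16–17% (true 90%, 16 subjects). With 24 subjects the rate was 1.6% at a true 85% and 0.3% at 80%. Variance was zero exactly when the estimate was 0% or 100%.

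**Effect on coverage, if the interval is r ± 1.96 SE (assumed; the SAP does not state the form).** In runs with non-zero variance, coverage was 99.8% and 99.5% in the first two scenarios. A zero-width interval at 100% never contains the true value, so overall coverage is about (1 − 0.26) × 0.998 = 74% and (1 − 0.17) × 0.995 = 83%. The shortfall there comes from the zero-width runs. Away from the boundary the loss is modest: about 91% coverage at true 80–85% with 24 subjects.

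**Where the method is used.** Primary table: 3 thresholds × 3 readers × 4 statistics = 36 lesion-level intervals. TAC: 4 types × 3 readers × 4 statistics = 48. Both sets are repeated in up to 8 subgroups (six tumour groupings and two immunotherapy groups). These counts show where the method applies, not how many cells will degenerate.

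**Combined criteria.** If the 'exact' wording in 7.4.4 means an ordinary exact interval that ignores clustering, it covers 95–98% when 15% of subjects have two lesions. If half do, it covers 94% (ICC 0.5) or 90% (ICC 1.0) at true 80% with 24 subjects.

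**The case against.** The algebra is not in dispute; the case against concerns weight.

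- **Frequency.** Zero variance is common only when the true rate is near the boundary or the denominator is small. At a true 85% or below with 24 subjects it is rare, as shown above. This stands, and the concern is limited accordingly.
- **Scope.** Not all subgroups can qualify under mild clustering. Melanoma, breast, lung, gastrointestinal and genitourinary do not overlap, so at 10 observations each they need 50; 40 subjects with 15% having two lesions give 40 × 1.15 = 46. This stands, and 8 is an upper limit.
- **The cited pages.** The textbook may give the step from variance to interval, and Appendix 1 may be only a worked example. That cannot be settled from the SAP. It would not remove the problem, because a normal or logit interval using only this variance still fails at the boundary.
- **The 'exact' sentence as fallback.** The SAP does not call it one. The lesion-level sentence replaces it, for a reason that an ordinary exact interval would not meet.
- **Visible and limited harm.** The counts of true and false positives and negatives are shown beside the interval. The subject-level exact interval covers the reference lesions, about 40/46 = 87% of all lesions under mild clustering. No test or success rule uses these intervals. All of this stands: it limits the consequence but does not supply the missing rule.
- **Choice of remedy.** The interval proposed below is one option among several, and it is conservative near the boundary. A one-line fallback at 0% and 100% would also close the gap.

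**Conclusion.** The point holds and should be fixed. As printed and coded, the lesion-level variance is zero at every estimate of 0% or 100%, and the SAP then leaves the interval degenerate or undefined. This is certain from the formula and needs no assumption.

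How often it will occur does rest on assumptions. It is roughly 17–29% per statistic at true rates of 90–95% with 16–24 contributing subjects, 53–74% with six contributing lesions at the same rates, and 2% or less at true rates of 85% or below with 24 subjects. Point estimates and subject-level exact intervals are unaffected. The study is descriptive, so the damage is overstated certainty in tables used to set reading criteria, not an invalid test.

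The unclear method for the lesion-level combined-criteria endpoint is a separate, minor clarification.

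**What to change.** In 7.4.3, name one boundary-safe, cluster-adjusted interval for all lesion-level statistics. For example, use Clopper-Pearson or Wilson limits on an effective sample size n_eff = r(1 − r)/Var, capped at the number of lesions, with n_eff set to the number of contributing subjects when Var = 0. In the one-wrong example above, n_eff = 0.964 × 0.036/0.00130, about 27, below the cap of 28. With all 24 subjects correct, n_eff = 24:

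- Clopper-Pearson lower limit: 0.025^(1/24) = 85.8%, giving 85.8–100%.
- Wilson lower limit: 24/(24 + 1.96²) = 86.2%, giving 86.2–100%.

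Across the simulated scenarios, including half of subjects with two lesions and ICC 0.5 to 1.0, the Clopper-Pearson version covered 95–99% and the Wilson version 93–97%. Another cluster method that behaves at the boundary would serve; what matters is fixing one in advance.

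In 7.4.4, add a sentence applying the same method to the lesion-level combined-criteria endpoint. Optionally, in 7.4.5.5, apply the 10-observation minimum to each statistic's own denominator.

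The cost is two or three sentences and a few lines of SAS. The downside is some wider, slightly conservative intervals: with 24 subjects, mean Clopper-Pearson width against r ± 1.96 SE is 0.21 v 0.14 at a true 95% and 0.34 v 0.31 at a true 80%.

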# 7.4.4 Secondary Endpoint Analysis Methods

In order to establish other image interpretation criteria for  $^{18}\text{F}$ -fluciclovine PET in detecting recurrent brain metastases, receiver operating characteristic (ROC) analysis of SoT against the quantitative measures of lesion  $^{18}\text{F}$ -fluciclovine uptake will be performed for each reader. A ROC curve will be produced for lesion SUV $_{\text{max}}$ , SUV $_{\text{peak}}$ , TBR $_{\text{max}}$  and TBR $_{\text{peak}}$ , with each point corresponding to a specific threshold, eg.  $\geq$  SUV $_{\text{max}}$  value vs < SUV $_{\text{max}}$  value. The AUC of each curve will be calculated using the trapezoidal method and will be annotated on the plot. Sensitivity, specificity, PPV, and NPV will be listed for each value of lesion SUV $_{\text{max}}$ , SUV $_{\text{peak}}$ , TBR $_{\text{max}}$  and TBR $_{\text{peak}}$ .

For TBRmax and TBRpeak, pairwise inter-rater agreement will be assessed using Pearson correlation coefficients.

For dynamic measures of lesion F-fluciclovine uptake represented by TAC type, applying each TAC category as a diagnostic criterion, estimates and the 95% exact confidence intervals for sensitivity, specificity, PPV and NPV for each of the 4 TAC types will be calculated and presented, by reader, on both subject and lesion levels. Lesion-level confidence intervals will be based on the method by Zhou et al..

In addition, pairwise inter-reader agreements at the lesion level for the 3 readers will be tabulated for TAC type. The proportions of agreement vs disagreement, Cohen's Kappa and the associated 95% confidence interval will be calculated.

These analyses will be reviewed by the separate Image Interpretation Committee to determine a set of image interpretation criteria based on the quantitative and dynamic measures.

Subsequently, for the diagnostic performance secondary endpoints, estimates and the 95% exact confidence intervals for sensitivity, specificity, PPV and NPV will be calculated based on the recommended thresholds from the following combination of interpretation criteria (if featured in the interpretation criteria):

- 1. Visual assessment of level of lesion F-fluciclovine uptake
- 2. Strongest performing quantitative measure (based on ROC analysis)

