#### Quantitative analysis

Lesion(s) and background structures will be outlined visually on static imaging data (e.g., from 10-20 minutes post-injection), and the measures recorded will include:

- lesion maximum standardized uptake value (SUVmax),
- lesion peak standardized uptake value (SUVpeak),
- background mean standardized uptake value (SUVmean),
- maximum tumor: background ratio (TBRmax; tumor SUVmax: SUVmean background),
- peak tumor: background ratio ( $TBR_{peak}$ ; tumor  $SUV_{peak}$ : background  $SUV_{mean}$ ).

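### Reader agreement on TBRmax and TBRpeak is judged only by Pearson correlation, which cannot detect one reader measuring consistently higher than another

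*SAP*

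**What the plan says.** Section 6.4.1.2 (Quantitative analysis) defines TBRmax and TBRpeak as lesion SUVmax or SUVpeak divided by background SUVmean, and says that "Lesion(s) and background structures will be outlined visually on static imaging data".

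Section 7.4.4 then uses four measures (SUVmax, SUVpeak, TBRmax, TBRpeak) in a ROC analysis for each reader, "with each point corresponding to a specific threshold". Sensitivity, specificity, PPV and NPV are listed for every value. The Image Interpretation Committee reviews these results to set quantitative criteria. The best quantitative measure by ROC may then enter the combined diagnostic performance analysis, "if featured in the interpretation criteria".

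On reader agreement for the two TBR measures, the whole provision is that "pairwise inter-rater agreement will be assessed using Pearson correlation coefficients". No confidence interval is mentioned. The categorical reads are treated differently: visual uptake (7.4.3) and TAC type (7.4.4) each get proportions of agreement and Cohen's kappa with a 95% confidence interval.

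**The concern.** The SAP calls the quantity agreement but computes linear association. Two readers agree on a continuous measure when they report nearly the same value for the same lesion. They correlate perfectly when one reader's values are any increasing straight-line function of the other's.

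The difference matters because the analysis looks for a numeric cut-off that can be used across readers. TBR has a reader-dependent denominator. A reader whose background outline gives consistently lower SUVmean values raises all of his or her TBRs by roughly a common factor. That leaves r unchanged, and it leaves that reader's AUC unchanged too, because AUC depends only on rank order. The two main summaries that the committee would see for TBR therefore share the same blind spot. A high r could be read as support for a common TBR threshold when the readers' thresholds in fact differ.

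**Working it through.** **No figure to reproduce.** The SAP states no agreement target, no expected TBR distribution and no candidate cut-off.

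**Step 1: invariance.** For any constant a and any b > 0, corr(X, a + bY) = b·cov(X, Y) / (SD(X)·b·SD(Y)) = corr(X, Y). A five-value example: reader A = 1, 2, 3, 4, 5.

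- B = A + 1: r = 1.00, Lin's concordance 0.80, absolute-agreement ICC 0.83.
- B = 2A: r = 1.00, concordance 0.42, ICC 0.48.

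**Step 2: size under proportional readers.** Assumptions, none from the SAP: reader A's TBR is log-normal with mean m = 2.5 and SD s; reader B = k × A exactly, with k > 1; the cut-off is c.

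- Concordance = 2ks² / (s² + k²s² + (m − km)²)
- Share classified differently at c = Φ((ln c − μ)/σ) − Φ((ln(c/k) − μ)/σ), where σ² = ln(1 + (s/m)²) and μ = ln m − σ²/2

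For s = 1.0: σ² = ln(1.16) = 0.1484, σ = 0.3853, μ = 0.9163 − 0.0742 = 0.8421.

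Worked case, k = 1.2: concordance = 2.4 / (1 + 1.44 + 0.25) = 2.4 / 2.69 = 0.89. Discordance at 2.5 = Φ(0.193) − Φ(−0.281) = 18.7%. Discordance at 4.0 = Φ(1.413) − Φ(0.939) = 9.5% (0.0949, shown as 9% in the table).

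| Ratio k | r | Concordance, SD 1.0 | Discordant at 2.5, SD 1.0 | Discordant at 4.0, SD 1.0 | Discordant at 2.5, SD 1.5 |
|---|---|---|---|---|---|
| 1.05 | 1.00 | 0.99 | 5% | 2% | 3% |
| 1.1 | 1.00 | 0.97 | 10% | 4% | 7% |
| 1.2 | 1.00 | 0.89 | 19% | 9% | 13% |
| 1.3 | 1.00 | 0.80 | 26% | 15% | 19% |
| 1.5 | 1.00 | 0.62 | 38% | 28% | 28% |

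With SD 1.5, concordance is higher: 0.94, 0.88 and 0.76 at ratios 1.2, 1.3 and 1.5.

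**Step 3: constant offset.** For an offset of 0.25 with SD 1.0, concordance = 2s² / (2s² + 0.25²) = 2 / 2.0625 = 0.97. Replacing c/k by c − 0.25 gives 11% discordant at 2.5 and 3% at 4.0. Again r = 1.00.

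**Step 4: random error added.** Each reader also has independent log-normal error with log-SD 0.10 (SD 1.0, simulated).

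| Ratio k | r | Concordance | Discordant at 2.5 | Discordant at 4.0 |
|---|---|---|---|---|
| 1.0 | 0.93 | 0.93 | 11% | 4% |
| 1.2 | 0.93 | 0.84 | 19% | 10% |
| 1.5 | 0.93 | 0.59 | 37% | 28% |

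The row with ratio 1.0 is random error alone. A 20% reader difference adds about 8 percentage points at 2.5 and 6 at 4.0. Pearson's r is the same in all three rows.

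**The case against.** The strongest reply is that the planned outputs already contain the information. ROC analysis is done for each reader, sensitivity and specificity are listed for each TBR value, and section 7.1.1 provides subject listings of collected and derived data in general. The committee that sets the cut-off reviews the per-reader analyses, so a shifted reader would show different sensitivity and specificity at the same TBR. This stands as a partial safeguard. It still leaves someone to compare lists by eye, with no paired difference, agreement figure or interval, while the statistic labelled agreement may look reassuring.

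Second, nothing in the SAP shows that a consistent reader difference will occur. For TBRmax the lesion outline hardly matters as long as it contains the hottest point, so an offset would come mainly from the background. Both points are right. They bear on how likely and how large the difference is, not on whether r could reveal it.

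Third, the stakes are low. The analysis is secondary and descriptive, r drives no decision, and the quantitative measure carried forward is chosen by ROC and used only if the criteria include it. This also stands, and it limits the weight of the point.

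**Conclusion.** The point holds. Pearson correlation is the wrong statistic for the stated purpose, and it is the only one planned for TBR. The invariance is exact and needs no assumption about the data.

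The practical size does rest on assumptions: the TBR distribution, the cut-off and the reader ratio are all illustrative. Within the range shown, differences of about 5% matter little (2% to 5% of lesions reclassified), 20% matters moderately (9% to 19%), and 50% matters a good deal (28% to 38%). Pearson's r does not separate these cases.

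This is a change to consider, not a threat to the trial. It touches two of four candidate quantitative measures in a secondary analysis and leaves the primary visual-read endpoint alone.

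**What to change.** In section 7.4.4, replace or supplement the Pearson coefficient for TBRmax and TBRpeak. For each reader pair, report:

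- Lin's concordance correlation or an absolute-agreement ICC, with a 95% confidence interval that allows for several lesions per subject, for example a bootstrap that resamples subjects. Section 7.4.3 already adjusts its lesion-level intervals "to account for clustering within subjects".
- The mean paired difference and limits of agreement on log-TBR, which express a reader difference as a ratio.
- Percent agreement at any TBR cut-off that the committee recommends.

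The first two items cure the defect; the third puts it in the terms in which a cut-off will be used. As a separate, optional addition, give the same figures for SUVmax or SUVpeak if one of them is carried forward, since section 7.4.4 plans quantitative agreement for TBR only.

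The cost is a wording change and modest programming on data already collected, most of it for the by-subject interval. The agreement figure will usually be lower than r, and with up to 40 subjects (section 7.6) its interval will not be narrow.

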### 5.2 Secondary Study Objectives

The secondary objectives of this study are:

- To establish other image interpretation criteria for F-fluciclovine PET in detecting recurrent brain metastases.
- To assess subject-level diagnostic performance of F-fluciclovine PET in detecting recurrent brain metastases.
- To assess lesion-level diagnostic performance of F-fluciclovine PET in detecting recurrent brain metastases.
- To assess the safety of F-fluciclovine injection in the subject population.

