For each subject, the final visit will usually be the preplanned SoC craniotomy/surgery at Visit 4. The subject will receive post-procedural management per institutional SoC. All ongoing follow-up and any further treatment will be in accordance with SoC and will not be recorded, including all medications and SoC procedure-related events occurring at and beyond Visit 4, and any SoC follow-up.

Subject-level standard of truth (SoT) will be defined by central histopathological diagnosis of the reference lesion. Lesion-level SoT will be defined by central histopathological diagnosis of all sampled lesions (reference lesions, MRI surgical lesions, additional PET lesions). Separately, central image analysis will define qualitative and quantitative lesion uptake of F-fluciclovine, for each resected lesion. These results will be reviewed by an Imaging Interpretation Committee to form image interpretation criteria.

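### The secondary diagnostic-performance estimates in SAP 7.4.4 come from the same subjects used to choose the criteria and are not designated as apparent performance

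*SAP*

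**What the plan says.** Four parts of the SAP fit together here.

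- **Data.** Section 7.4.1 bases every efficacy summary on the Imaging Evaluable Analysis Set (IEAS). Section 7.6 plans up to 40 enrolled subjects, so the IEAS can be no larger.
- **Choosing the criteria.** Section 6.1, after describing central histology and central uptake measurement, says "These results will be reviewed by an Imaging Interpretation Committee to form image interpretation criteria". Section 7.4.3 says the results for the three visual thresholds "will be reviewed by the separate Image Interpretation Committee as described in the study protocol to determine image interpretation criteria based on visual reads". Section 7.4.4 has the ROC and time-activity-curve results "reviewed by the separate Image Interpretation Committee to determine a set of image interpretation criteria based on the quantitative and dynamic measures".
- **Scoring the criteria.** Section 7.4.4 continues: "Subsequently, for the diagnostic performance secondary endpoints, estimates and the 95% exact confidence intervals for sensitivity, specificity, PPV and NPV will be calculated", and this is to be "based on the recommended thresholds from the following combination of interpretation criteria (if featured in the interpretation criteria". The two listed components are the visual uptake level and the "Strongest performing quantitative measure (based on ROC analysis".
- **What the figures are for.** Section 5.2 has two secondary objectives that begin "To assess subject-level diagnostic performance of" and "To assess lesion-level diagnostic performance of". Neither carries a qualifier about data reuse.

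The SAP mentions no hold-out sample, resampling or second cohort for this step. It does not describe the resulting figures as apparent performance.

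**The concern.** A rule chosen because it separates tumor from non-tumor well in a sample will, on average, look better in that sample than in new patients. The candidates here are three visual thresholds and four quantitative measures (SUVmax, SUVpeak, TBRmax, TBRpeak). For each measure, performance is listed at every observed value. For the measure itself, the SAP says outright that the best by ROC is taken.

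An exact binomial interval assumes that the threshold did not depend on the data being scored. Without a label, a reader of the results tables may take the sensitivity, specificity, PPV and NPV as the performance to expect in new patients.

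**Working it through.** **No figure to reproduce.** The SAP gives no performance target, prevalence, AUC or committee rule. The size is therefore explored under assumptions, all outside the SAP.

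**Model.** Uptake is normal with equal variances in tumor and non-tumor, separated by δ. Then AUC = Φ(δ/√2), so δ = √2·Φ⁻¹(AUC). At cut-off c, true sensitivity = 1 − Φ(c − δ) and true specificity = Φ(c). Optimism = apparent value in the trial minus true value of the rule that was chosen.

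**Step 1: a ceiling check.** For one measure, the best possible sum of sensitivity and specificity is at c = δ/2, where both equal Φ(δ/2). The table compares this with simulated averages for N = 40, recurrence 60%, best of four measures (correlation 0.80) by AUC, then the Youden cut-off (4,000 runs each).

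| AUC | δ | Ceiling Φ(δ/2) | Apparent sens / spec | True sens / spec of chosen rule |
|---|---|---|---|---|
| 0.70 | 0.742 | 64.5% | 73% / 75% | 63% / 63% |
| 0.80 | 1.190 | 72.4% | 80% / 82% | 71% / 72% |
| 0.90 | 1.812 | 81.8% | 88% / 90% | 80% / 81% |

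The average apparent values exceed what any cut-off on the measure can truly achieve for both metrics together. The chosen rule falls slightly below that ceiling.

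**Step 2: optimism by selection rule.** Subject level, N = 40. Tumor/non-tumor splits 26/14, 20/20 and 30/10; AUC 0.70, 0.80 and 0.85; measures correlated 0.9; visual scale correlated 0.8 with them. Apart from the stated-step row, which uses one reader, results cover one reader or one rule shared by three readers.

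| What is chosen from the data | Sensitivity (points) | Specificity (points) |
|---|---|---|
| Nothing (visual threshold fixed in advance) | 0.0 | 0.0 |
| Visual threshold, sensitivity at least 85% first | −0.3 to 1.6 | −0.7 to 0.8 |
| Visual threshold, maximum Youden | 1.2 to 3.8 | 2.2 to 6.7 |
| Best of four measures only, cut-off fixed in advance (the step the SAP states) | 1.0 to 2.3 | 1.8 to 4.2 |
| Visual plus quantitative cut-off, sensitivity-first | 1.3 to 5.9 | 1.0 to 3.1 |
| Visual plus quantitative cut-off, Youden on each, better of AND/OR | 3.5 to 9.8 | 4.7 to 15.3 |
| Joint search over all combinations | 4.4 to 12.4 | 6.1 to 18.2 |

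Worked case (26/14, AUC 0.80, one reader, Youden on each part): sensitivity 78.8% apparent against 72.3% true, a gap of 6.5 points; specificity 81.0% against 70.5%, a gap of 10.5 points.

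At lesion level (26/14, with 5, 10 or 20 extra lesions), Youden gives 1.1 to 2.8 and 2.2 to 5.3 points for the visual threshold alone. For the combined rule it gives 3.4 to 6.9 and 5.1 to 11.1.

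**Step 3: interval coverage.** Subject-level coverage of the nominal 95% exact interval is 95 to 99% for visual-only criteria and 92 to 98% for the combined rule. For a quantitative cut-off alone it is 90.5 to 98%. With measures correlated only 0.80 and N of 30 or 40, coverage for sensitivity falls to about 88 to 93%. Coverage holds up because the intervals are wide: 21/26 gives 60.6% to 93.4%, and 11/14 gives 49.2% to 95.3%.

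**Step 4: does leaving subjects out help?** Repeating the whole choice with each subject left out (Youden rule) lowers the average absolute mean bias from 8.8 to 1.5 points (combined, one reader) and from 6.1 to 0.5 (combined, shared rule). For the visual threshold it falls from 3.8 to 1.2 (one reader) and from 2.5 to 0.7 (shared rule). But its root mean squared error exceeds that of the apparent figure in 66 of 72 subject-level and 24 of 24 lesion-level comparisons.

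**The case against.** **The design is open about itself.** The title and primary objective say the study establishes criteria, and 7.4.4 states the order of steps. Reuse is normal in phase 2b, and no passage calls the result validated. This stands. A reader might infer that the reuse is invalid or that the SAP claims validated performance; the document supports neither. What is left is that two secondary objectives assess performance, and the text defining that analysis does not say what kind of performance it yields.

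**Section 7.4.5.4 already says there is no multiplicity adjustment.** True, but that does not tell the reader that the scored thresholds were picked from the same data.

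**The protocol may hold the committee's rule or a caveat.** Possibly; 7.4.3 refers to it, and it is not at hand. The caveat still belongs where the estimates are defined.

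**The size comes from assumed rules.** This stands. The SAP fixes only the choice of measure by ROC. That step alone gives about 1 to 4 points, and the quantitative part enters only if featured. It would be wrong to infer that this trial's figures will be off by 10 points or more.

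**The intervals mostly cover.** This stands too. The coverage concern is confined to a quantitative cut-off and is modest there.

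**Leave-one-out is noisy and corrects only a surrogate rule.** Correct. Within one trial, the gap between the two figures is almost uncorrelated with the actual optimism (r from −0.22 to 0.09). It is therefore supportive only, and not a measure of this trial's bias.

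**Conclusion.** The point holds as a minor one. Section 7.4.4 scores the established criteria in the IEAS subjects whose histology results were used to choose them, with intervals that take the chosen thresholds as given and no statement to that effect. If selection favours what does well in these data, the estimates are optimistic on average, although a single metric may be traded off against another.

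The size is not derivable from the SAP. With N = 40 and a Youden-type choice it is roughly 2 to 7 points for a visual threshold alone and roughly 5 to 15 when a quantitative cut-off is added. Under a sensitivity-first visual rule it is near zero. Subject-level interval coverage is near nominal for visual-only criteria and modestly low at worst with a quantitative cut-off. These figures rest on the assumed prevalence, AUC, correlations and selection rules listed above.

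The primary analysis reports every visual threshold, and the study has no hypothesis test or success rule, so nothing there is affected.

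**What to change.** In section 7.4.4:

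1. State that these estimates and intervals are apparent performance in the subjects used to set the criteria, are not adjusted for selection, and will not be concluded as validated performance.
2. As a supportive sensitivity analysis only, report leave-one-subject-out estimates beside them. Leave out all lesions of a subject together, and repeat the choice of threshold, measure and cut-off each time under a surrogate rule fixed before unblinding to the standard of truth. Say that this corrects the surrogate rule and not the committee's judgement, and that the gap does not measure this trial's own optimism.

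Item 1 costs a sentence. Item 2 costs one extra program and no new data. The downside is a second set of less favourable and usually noisier figures beside the main ones. If only one item is adopted, it should be the first, which does not depend on the second.
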